9.7. Blinding and code-breaking

This is a single arm study evaluating nceMRI and USS as tests for HCC surveillance. The blinding procedures in the study will therefore focus on ensuring the acquisition and reporting of USS and nceMRI are blinded from each other.

Timing of USS and nceMRI acquisition and reporting

USS are usually performed and reported by the same operator. It is therefore usual practice for USS to be reported immediately after the acquisition of the data. On the other hand, nceMRI scans are usually acquired by MR radiographers and an MR radiologist reports on the data subsequently. There may therefore be an interval between acquisition and reporting of nceMRI data. For the purposes of this study, surveillance USS and nceMRI should preferably be acquired on the same day. Reports for both tests should be available to the clinical team within 4 weeks of the first scan being acquired. Therefore, the second scan can be acquired up to 4 weeks after the first scan, but in this case, the second scan must be reported on the same day it is acquired.

Blinding procedure

In any surveillance round, the surveillance test that is acquired first, will be labelled with and reported under the AMULET study identifier. This will ensure that the report and images for the first surveillance test are kept separate from the electronic patient record and the radiology department PACS systems and will not be available to the radiologist reporting the scan being performed second at each 6 monthly surveillance episode. Once the second scan is reported then the images and report of the first test will be un-blinded and uploaded to the electronic patient record and PACS system.

- 1. First scan is performed either USS or nceMRI
 - a. Scan is labelled and reported using AMULET study ID only no personal identifiers should be included
 - b. Report proforma is completed and entered into study database
 - c. The report and images should not be uploaded to the electronic patient record or radiology department PACS system at this point
- 2. Second scan is performed within 28 days either USS or nceMRI (whichever was not performed as the first scan)
 - a. Patient identifiers may be used and report/images uploaded as normal
- 3. After reporting of the second scan is complete, the report/images from the first scan should be un-blinded and uploaded to the electronic patient record and PACS system.

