9.8.2. Description of study procedure(s)

Collection of Demographics and Medical History

A member of the study team will access the medical notes of the participant to obtain information about the individual's demographics, medical history, anthropological measurements (height, weight and resulting BMI) and previous clinical imaging data.

Participant questionnaires

Participants will be asked to complete paper copies of the EQ-5D-5L questionnaire and Hospital Anxiety and Depression Scale (HADS) at each research visit, and a study specific participant experience questionnaire relating to USS and nceMRI at the baseline visit and visit 5. Data will be transferred from the completed paper copies to the study electronic case record form by the site study investigators.

Ultrasound scan

USS reporting for the imaging findings

Ultrasound scans are performed as part of the participant's routine clinical care. Surveillance USS findings will be interpreted and reported by appropriately trained and experienced sonographers or radiologists at each site, who will receive training in study specific assessments and documentation, including the blinding process. Each USS episode will have a findings category score assigned using the US LI-RADS³⁷ reporting system (US1-negative; US2 subthreshold; US3 positive)."US1- negative" examinations will be those where no suspicious observations are noted, or where there are only definite benign observations. "US3 -positive" examinations will be those with an observation ≥10mm in diameter

that is not definitely benign, including areas of parenchymal distortion or new thrombus in the portal vein or hepatic vein. "US2 subthreshold" examinations will be those with observations <10mm in diameter that are not definitely benign.

"US1- negative" will be designated as negative examinations for the purposes of our study. Participants will return for 6 monthly surveillance after an "US1-negative" examination.

"US3 positive" will be designated as positive examinations for the purposes of our study and will be followed up by a full contrast enhanced MRI scan.

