A study visit that takes place within 30 days of the designated visit date will be regarded as a visit that took place on time. Accepting that there will be instances where there are last minute cancellations due to unforeseen circumstances and to allow flexibility in these situations, out of schedule visits will be permitted. Visits taking place between +30 and +90 days of the scheduled visit will be counted as a delayed visit. If the visit cannot be organised within the 90-day window then the visit will be regarded as missed and any procedures taking place more than 90 days after the scheduled visit time, will be assigned as subsequent visit procedures. This schedule will ensure that all study visits are completed within the 30-month window of follow-up.

If only one scanning procedure is performed within the designated visit window, this will be classed as a missed visit.

Examples of study visit timings are set out in Figure 3 below.

Visit 5 – Day 631 (+30)

nceMRI Scan

Visit schedule resets from date of early visit

(D271 +180)

nceMRI Scan

Visit 4 – Day 451 (+30)

Ultrasound Scan

Ultrasound Scan

Visit 6 - Day 811 (+30)

Contrast enhanced MRI Scan

nceMRI Scan

Ultrasound Scan

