11.7. The Level of Statistical Significance

Statistical significance will be set at p<0.05.

11.8. Procedure for Accounting for Missing, Unused, and Spurious Data.

Participants must attend the baseline and last visit (v6) and have at least one ceMRI (after a positive surveillance test, or as per protocol at the end of the study period) in order to be included in the final analysis. Participants who do not meet this will be removed and replaced for the purposes of the statistical analysis. All data from participants that fulfil this criterion will be used and analysed using intention to diagnose methods. This is to ensure that cases where a participant completes one surveillance test but not the other at a particular visit are still included. The diagnostic category of the missed test will be determined according to the diagnosis on that visit and the final diagnosis at the end of the study. In cases of HCC diagnosis, the missed test will be assigned as FN. In cases of FP results on the surveillance test performed at that visit, the missed test will also be assigned as FP.

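### Section 9.7 releases the blinded first scan only once the second scan is reported, with no release step if the second scan is late or never done

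*Protocol*

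**What the plan says.** Section 9.7 (Blinding and code-breaking) labels and reports the first scan of a round under the study identifier only. Step 1b gives the report a destination: "Report proforma is completed and entered into study database". Step 1c sets the hold: "The report and images should not be uploaded to the electronic patient record or radiology department PACS system at this point". Step 2 requires the second scan within 28 days.

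Release is described twice, with the same trigger. The narrative says "Once the second scan is reported then the images and report of the first test will be un-blinded", and step 3 says "After reporting of the second scan is complete, the report/images from the first scan should be un-blinded and uploaded to the electronic patient record". The section also states a time target: "Reports for both tests should be available to the clinical team within 4 weeks of the first scan being acquired". From that target it infers that the second scan may follow up to 4 weeks later, provided it is then reported the same day.

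Three other places bear on the point:

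- **One-scan visits are expected.** Section 9.10: "If only one scanning procedure is performed within the designated visit window, this will be classed as a missed visit". Section 11.8 keeps such participants in the analysis and gives its reason: "This is to ensure that cases where a participant completes one surveillance test but not the other at a particular visit are still included".
- **A positive test leads to ceMRI.** Section 9.8.2 says this for a US3 ultrasound. Section 9.10 and the footnote to Appendix A say it for either test.
- **The ultrasound is not a research extra.** Section 9.8.2: "Ultrasound scans are performed as part of the participant's routine clinical care".

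**The concern.** The hold exists to keep the second reader unaware of the first result, which is sound for a paired accuracy comparison. The difficulty is that its end depends on an event that the protocol itself expects will sometimes not occur. If the second scan is cancelled, abandoned or missed, the release step has nothing to trigger it.

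Two things are at stake. The first is patient safety. The held scan may be the routine-care ultrasound, which section 9.7 notes is usually reported immediately, in a cohort selected mainly for an annual HCC risk of at least 3%. The second is the primary outcome. Section 11.2 can classify positives as true or false at each round because every positive is followed by ceMRI. A positive that does not reach the team arranging the ceMRI has no verified status at that round, and a tumour behind it may surface later or at a later stage.

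**Working it through.** No sample size, power or error rate bears on this, so the check sets the rules side by side and follows one visit through them. Count days from acquisition of the first scan, and let d be the day on which the second scan is done.

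1. **Both scans on schedule (d from 0 to 28).** If the scans are on different days, the second must be reported on the day it is acquired, so step 3 releases the first scan on day d. The longest hold is 28 days, and 4 weeks × 7 = 28 days. If both are done on the same day, the 4-week target still governs the reporting. Here the release step and the target agree.

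2. **Second scan late (d greater than 28).** This already departs from step 2. Step 3 nevertheless keeps holding the first scan until the second report exists, so the hold exceeds 28 days and the 4-week target is missed. No step says that the first scan is released at day 28 when the second is outstanding.

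3. **Second scan never done.** Step 3 has no trigger, and the written procedure gives no release date. The 4-week statement still says that the clinical team should have the report. The two cannot both be followed.

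Next, does any other section supply the missing step for cases 2 and 3?

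- Section 9.10 gives the one-scan visit a status (missed) but says nothing about the scan that was done.
- Section 11.8 gives it an analysis rule. The missed test is assigned as a false negative if HCC is diagnosed, and as a false positive if the scan performed was a false positive. Both assignments presuppose that the single positive scan was followed up. Nothing in section 9.7 ensures that.
- Sections 9.8.2 and 9.10 and Appendix A require ceMRI after a positive test but do not say how a held report reaches whoever requests it.
- The closing paragraph of section 9.7 replaces the blinding steps with a reader's confirmation, but only at sites that cannot implement them for logistical reasons. It is not a release rule for sites that do implement them.
- Section 9.13 allows withdrawal at any time and allows the investigator to stop study MRI. It does not mention a scan being held at that moment.

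No section fills the gap.

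**Size.** The planned denominator is 300 participants × 6 visits = 1,800 visits, before attrition and exits after HCC. The protocol gives neither a one-scan rate nor a per-scan positive rate, so the number of affected visits cannot be calculated from it.

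**The case against.** The best defence is that the intent is clear and the exposure narrow. Same-day scanning is preferred, the gap is limited to 28 days, and a 4-week target for both reports is stated. The purpose given for the hold is to keep the first result from the radiologist reading the second scan; nothing expressly blinds the investigator or the clinician. The report is in the study database from the start. The duty to perform ceMRI after a positive test does not depend on upload to the record. Sensible site staff would pass on a suspicious finding.

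Much of this stands, and it rules out several stronger readings that a reader might infer:

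- **That the result is hidden without limit, or lost.** The 4-week statement is a limit, and the report exists in the study database. What is missing is a step that carries out the limit when there is no second report.
- **That the visit window allows a hold of up to 120 days, from 30 days before the scheduled date to 90 days after it.** The window in section 9.10 places a visit relative to its scheduled date. The gap between the two scans of a visit is a separate interval, capped at 28 days in sections 9.7, 9.9 and 9.10. A delayed visit moves the pair of scans and does not stretch the gap, so the two rules do not conflict.
- **That the number of withheld positives can be estimated from section 11.3.** That would need an invented one-scan rate. It would also read as per-scan figures specificities that section 11.2 defines once per participant over 30 months.

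The defence does not supply the missing step. Staff who passed on the result before a second report existed would be acting outside step 3, and no instruction tells them to do so.

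**Conclusion.** The point holds in a limited form. When the second scan is late or absent, step 3 of section 9.7 conflicts with the same section's 4-week statement and leaves the ceMRI requirement without a stated route for the result. This is a written rule that fails in a situation the protocol expects, and so more than a detail left for later documents.

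When both scans are on schedule there is no conflict and the hold is at most 28 days. When the second scan is never done, the steps set no release date. The frequency is unknown, and the conclusion does not depend on it, since a single positive scan at a one-scan visit is enough to expose the conflict. It assumes that sites follow the numbered steps as written; sites working under the logistical exception may not withhold the report at all.

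**What to change.** Reconcile step 3 of section 9.7, and the matching narrative sentence, with the section's own 4-week statement and with sections 9.8.2, 9.10 and 11.8 and Appendix A. Release of the first scan should not depend solely on a second report that may never exist. State in the same place who passes on the held report. Whether a particular finding, a cancellation or a withdrawal calls for earlier release is a clinical matter for the sponsor and clinical leads to decide.

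A second scan read after the first has been released can use the reader confirmation already provided at the end of section 9.7.

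The cost is about one sentence in section 9.7 and a reminder in the study database. The small downside is that a few late second reads would rest on self-declaration instead of physical blinding.

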9.8. Description of study intervention(s), comparators and study procedures (clinical)

This a non-interventional study.

9.8.1. Description of comparator(s)

The comparator will be the diagnosis of hepatocellular carcinoma based on the typical features on contrast enhanced MRI or CT or histological diagnosis (biopsy or resection) or a consensus diagnosis of HCC as determined by the local MDT will be accepted as a diagnosis of HCC.

On study contrast enhanced MRI scans

For cases where a contrast enhanced MR is done following a positive surveillance test (on study ceMRI), lesions classified as LI-RADS 1 or 2 will be regarded as negative for HCC and lesions classified as LI-RADS 5 will be regarded as positive for HCC. Lesions classified as LI-RADS 3 or 4 will be regarded as indeterminate and will be followed up according to the local clinical routine. If LI-RADS 3 or 4 are designated as HCC by the local MDT, or they are proven to be HCC on biopsy, or they progress to LI-RADS 5 within the 30 months of follow-up then they will be defined as HCC for the analysis relating to the whole 30 month period of surveillance. In cases where LI-RADS 3 or 4 lesions remain under follow-up at the end of the 30 months follow-up without a clear classification as HCC or benign, or where they have been histologically proven to be benign, then they will be classified as negative for HCC for the purposes of the analysis. The classification of lesions at on-study ceMRI scans is shown below in Figure 2. The follow-up of LI-RADS 3 and 4 lesions in this situation will finish at the timepoint that visit 6 was due or at an earlier time point if a definitive classification is reached before then.

Figure 2: Flowchart for the classification of lesions detected on contrast enhanced MRI performed during the study following a positive surveillance test. In cases where lesions are determined as negative within the 30-month surveillance period, participants will re-enter the AMULET surveillance schedule until they complete the study. Where a positive for HCC diagnosis is made, participants will end their participation, will undergo no further surveillance and will be managed according to the recommendations of the local MDT. Participants with LI-RADS 3 or 4 lesions who are undergoing interval contrast enhanced imaging as recommended by the local MDT will be suspended from participation in AMULET.

End of Study contrast enhanced MRI scan

Participants that complete all 6 rounds of surveillance without a positive surveillance test and without HCC will undergo a contrast enhanced MRI at the end of the study (end of study ceMRI). The diagnostic allocation schedule will be modified for these scans as there will be no opportunity to follow-up LI-RADS 3 and 4 lesions. In these scans LI-RADS 1, 2 and 3 will be classed as not HCC and LI-RADS 4 and 5 lesions will be classed as HCC.

Follow-up for indeterminate lesions beyond 30 months

To enable potential future research, participant consent will be sought to allow follow-up through medical records or through data provided from NHS England, the NHS Central Register for Scotland and other patient registries for up to 10 years after their study participation is completed. This is to allow for collection of data relating to lesions that are still indeterminate at the end of 30 months surveillance period and to evaluate if those without HCC at the end of the study still go on to develop HCC. To facilitate this follow-up, personal identifiable information will be collected and stored centrally with participants' permissions.

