Design and Methods: We will recruit 300 people at higher risk of developing liver cancer because of cirrhosis. Study participants will have an ultrasound scan every 6 months as they would in their standard clinical care and an additional 6 monthly non-contrast MRI scan for 30 months (6 visits). If the ultrasound or non-contrast MRI raises concern for a possible liver cancer, an MRI scan with contrast (with dye injection) will be done for definitive diagnosis. All participants will have an MRI with contrast at the end of 30 months to ensure that no cancers were missed. Participants will be asked to complete questionnaires to measure quality of life, anxiety, and their experience of MRI and ultrasound scans and data will be collected from their medical notes. We will compare the number of liver cancers detected by ultrasound to the number detected by the non-contrast MRI scans.

Follow up data will be collected from NHS England, the NHS Central Register for Scotland and other patient registries for up to 10 years after the last study MRI scan to determine the long-term outcomes of participants.

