7. STUDY DESIGN

This will be a single-arm, multi-centre, prospective cohort study evaluating the diagnostic accuracy of nceMRI and USS for diagnosis of HCC in people at high risk of HCC. People at high risk of HCC include those with liver cirrhosis and a high risk of HCC, or those with previous successfully treated HCC who are back in surveillance with USS. Participants will be recruited from UK hospital-based liver clinics over a period of 18 months and study procedures will take place in UK hospitals and academic centres. Participants will undergo 6 rounds of 6 monthly surveillance with nceMRI and USS over 30 months. Participants will be invited to complete questionnaires at each study visit. Relevant data will also be extracted from the participants' medical records. If at any surveillance round, a surveillance test raises a concern for the presence of HCC, participants will undergo full diagnostic contrast enhanced MRI (ceMRI) to determine whether HCC is present or not. In cases where indeterminate lesions for HCC are reported, these may require further tests including contrast CT, follow-up contrast enhanced MRI, or biopsy as directed by the clinical team. All participants will undergo diagnostic full contrast enhanced MRI at the end of their study participation. If an HCC is diagnosed at any point in the study, then participants will receive treatment according to standard clinical protocols as part of standard of care.

Long-term follow up of medical records from NHS England, the NHS Central Register for Scotland and other patient registries may be conducted for up to 10 years after the end of the active follow up phase. Data obtained from these registries will include but is not limited to liver disease, decompensation episodes, HCC diagnosis, liver transplantation and death. There will be no additional involvement from study sites or participants, as the long-term follow up only involves accessing centrally held medical data.

The overall study design and participant flow is summarised in Figure 1.

Figure 1: AMULET study design and patient flow

Abbreviations: HCC: hepatocellular cancer; USS: ultrasound scan; nceMRI: non-contrast enhanced MRI; AFP: alpha-fetoprotein; HADS: hospital anxiety and depression scale; +ve: positive; -ve: negative [#] see section 9.4 for the description of the procedure for HCC risk estimation

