9.10. Subsequent Study Visits

At each subsequent visit, the patient's eligibility to the study will be checked and patients will undergo another formal safety assessment before undergoing MR examinations. Patients will have to attend their MRI having fasted for at least 4 hours.

Each follow up visit will ideally take place on a single day but may take place on two separate days, with the first imaging scan and data collection taking place up to 28 days prior to the second imaging scan (see also section 9.7).

Participants will attend follow-up every 180 days for five visits after baseline (total of six visits including baseline). At each subsequent visit, confirmation of continuous consent will be obtained from the participant and an eligibility check will be carried out to ensure that participants still fulfil the inclusion and exclusion criteria.

Study visits will last for 120 minutes and assessments/procedures are as follows:

- Collection of Demographics and Medical History (duration 10 minutes)
- Physical Examination (recording of height and weight) (duration 5 minutes)
- Completion of MRI safety check (5 minutes)
- Clinical care USS (20 Mins)
- nceMRI (20 minutes)
- Completion of EQ-5D-5L and HADS questionnaires at the beginning of each study visit (30 minutes)
- Acceptability of MRI and USS as surveillance test questionnaire (to be completed immediately after the relevant scan on visit 5 only, 30 minutes)

Visit 6, final study visit (120 minutes)

At visit 6, in addition to the other study procedures listed above, a contrast enhanced MRI will be performed on all participants.

Contrast enhanced MRI will also be performed at any visit if the surveillance USS or nceMRI show a suspicious nodule for HCC.

Timing between visits

The baseline visit (visit 1) will be designated as D0. If the study procedures take place on different days for the baseline visit then D0 will be the first day on which study procedures were carried out. Once the baseline visit is completed, dates will be assigned for subsequent visits (visit 2: D180, visit 3: D360; visit 4: D540 etc).

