11.2. Description of the Statistical Methods

Statistical analysis for Primary outcome measure

Measures of diagnostic performance will be determined per round of surveillance and over the 30 months of study participation.

Diagnostic performance per round of surveillance

At each round of surveillance, the following data will be calculated and compared between USS and nceMRI.

- 1. Number and proportions of positive surveillance USS and nceMRI see section 9 for definitions of positive tests
- Number and proportions of true positive (TP) and false positive (FP) USS and nceMRI. As each positive test will be followed by a full contrast enhanced MRI, TP and FP tests per round of surveillance will be calculated
- 3. Positive predictive value (PPV) of USS and nceMRI

Diagnostic performance for the overall study period of 30 months

For the purpose of this analysis, each USS and nceMRI scan for each participant completing the study will be assigned only one of the 4 possible diagnostic categories of: true positive (TP) or false positive (FP), true negative (TN) and false negative (FN). The sum of TP, FP, TN and FN in this analysis will therefore be equal to the total number of participants completing the study. TP and FP will be determined at each visit as described above. TN and FN will be determined at the end of the study when participants undergo the reference standard ceMRI as part of the study protocol. FN results will also include those cases that present with HCC during the study without a prior positive test (interval cancers) or cases where both USS and nceMRI are negative tests but a ceMRI scan is triggered by an AFP>20. Cases that are initially FP may subsequently change diagnostic category. For this analysis, the diagnostic category which is applicable at the end of the study will be used. For example, if a finding initially classed as an FP develops into an HCC that was correctly identified by the surveillance tests, then the diagnostic test will be counted as a TP for this analysis.

Sensitivity and specificity estimates will be calculated separately for nceMRI and USS and compared. Statistical significance of the observed differences in sensitivity/specificity will be evaluated using the McNemar's test of paired proportions, with a two-tailed P-value <0.05 used as the significance criteria.

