22. APPENDIX A: SCHEDULE OF STUDY PROCEDURES

Procedures	Visits								
	Visit timing -360 days to Day 0 Screening	Baseline Day 0 (+28) Visit 1	Day 180 ±30 days Visit 2	Day 360 ±30 days Visit 3	Day 540 ± 28 days Visit 4	Day 720 ± 30 days Visit 5	Day 900 ±30 days Visit 6		
								Informed consent/continuous consent	
Demographics		x							
Medical history		x	x	x	x	x	x		
Physical examination		x	x	x	х	x	x		
MRI Safety Checks		x	x	x	x	x	x		
Case notes review	x	x	x	x	х	x	x		
Eligibility assessment Inclusion / exclusion criteria aMAP score calculation	x								
Standard of care liver USS		x	x	x	x	x	x		
Liver nceMRI		x	x	x	x	x	x		
Contrast enhanced liver MRI		*	*	*	*	*	x		
HADS		x	x	x	х	x	x		
EQ-5D-5L		x	x	x	x	x	x		
Patient experience questionnaires		x				x			
Adverse event assessments		x	x	x	х	x	x		

* A contrast enhanced liver MRI scan is mandatory at visit 6 and must be performed at any of the study visit standard of care ultrasound scan or non-contrast enhanced MRI scan show possible hepatocellular cancer

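### Section 9.8.1 ties the end-of-study ceMRI to having had no earlier positive test, four other places give it to everyone, and section 11.8 lets an earlier triggered scan stand in for it

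*Protocol*

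**What the plan says.** **Who has the end-of-study scan.** Section 9.8.1, under its end-of-study ceMRI heading, describes a restricted group: "Participants that complete all 6 rounds of surveillance without a positive surveillance test and without HCC will undergo a contrast enhanced MRI". Four places set no such condition:

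- Lay summary: "All participants will have an MRI with contrast at the end of 30 months to ensure that no cancers were missed".
- Section 7: "All participants will undergo diagnostic full contrast enhanced MRI at the end of their study participation".
- Section 9.10, visit 6: "a contrast enhanced MRI will be performed on all participants".
- Appendix A, footnote: "A contrast enhanced liver MRI scan is mandatory at visit 6".

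**What the analysis needs.** Section 11.2 states that "TN and FN will be determined at the end of the study when participants undergo the reference standard ceMRI". It adds that a case first classed as false positive may change category, and that the category at the end of the study is the one used.

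**What the analysis accepts.** Section 11.8 requires attendance at baseline and visit 6, and that participants "have at least one ceMRI (after a positive surveillance test, or as per protocol at the end of the study period"). It sets no limit on how long before visit 6 a triggered scan may have been done.

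**Who is affected.** Section 9.8.1 provides that when a triggered ceMRI shows no HCC, "participants will re-enter the AMULET surveillance schedule until they complete the study". A participant with an early false positive can therefore complete all six rounds and still fall outside the group that 9.8.1 describes for the final scan.

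**The concern.** The final scan establishes who was free of HCC and who had a cancer that surveillance missed. If it goes only to participants who never tested positive, verification at month 30 depends on the results of the tests under evaluation. A cancer that arises after a false positive, and is then missed by both tests, would be counted as no HCC. That removes false negatives and raises the apparent sensitivities.

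The loose wording in 9.8.1 would matter less if the analysis rule caught it. It does not: the alternative in 11.8 allows a triggered scan from an early round, up to about 30 months old, to satisfy the inclusion rule. A scan not done at visit 6 cannot be recovered at analysis.

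A second ambiguity follows. Section 9.8.1 has two rules for allocating lesions. On a scan triggered during the study, a LI-RADS 4 lesion still unresolved at 30 months counts as negative. On the end-of-study scan, LI-RADS 4 counts as HCC, but that rule is written for the never-positive group. The protocol does not say which rule applies to a previously positive participant scanned at visit 6.

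**Working it through.** **Inputs.** From section 11.3: specificity 80% (nceMRI) and 90% (USS); sensitivity 80% and 50% as one planning pair; 50 HCCs; about 250–300 controls; McNemar's test with 90% power and 5% type 1 error. From section 8.2: annual HCC risk of at least 3%. The protocol states no correlation between the tests.

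**Step 1: reproduce Table 2.** With p11 = p1·p2 + ρ·√[p1(1−p1)p2(1−p2)], ψ = p1 + p2 − 2·p11 and d = |p1 − p2|, the paired formula is n = [1.960·√ψ + 1.2816·√(ψ − d²)]² / d².

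- Sensitivity 80% v 50%, ρ = 0.1: p11 = 0.42, ψ = 0.46, n = 49.4, rounded up to 50. Table 2 gives 50.
- Specificity 80% v 90%, ρ = 0.1: p11 = 0.732, ψ = 0.236, n = 243.8, rounded up to 244. Table 2 gives 244.

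With ρ = 0 the results are 55 and 270. The value ρ = 0.1 matches 15 of the 16 numeric cells. It is inferred from the table, so the range over possible overlaps is shown below.

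**Step 2: HCC-free participants with at least one false positive.** The share is 0.20 + 0.10 − (both tests false positive).

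| Overlap of false positives | Share | Of 250 | Of 300 |
|---|---|---|---|
| Complete (joint 0.10) | 20% | 50 | 60 |
| ρ = 0.1 (joint 0.02 + 0.1 × 0.12 = 0.032) | 26.8% | 67 | 80 |
| None (joint 0) | 30% | 75 | 90 |

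This reads the specificities as per participant over 30 months, as section 11.2 calculates them. The counts are an upper limit for those without current imaging. A false positive at visit 6 triggers a scan then, and participants with LI-RADS 3 or 4 lesions may be under interval contrast imaging until visit 6 was due.

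**Step 3: HCCs that could be hidden.** The participants in Step 2 are HCC-free, so none of them is a hidden case. As an approximation, apply the HCC risk to a group of 67.

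- At 3% a year with 6 months left after the triggered scan: 67 × (1 − 0.97^0.5) = 1.0.
- With 24 months left: 67 × (1 − 0.97²) = 4.0.
- Upper case, with every false positive at baseline and the planned yield of 50 in 300: 67 × 50/300 = 11.2.

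An HCC stays hidden only if both tests miss it. At 80% and 50% with ρ = 0.1: 0.2 × 0.5 + 0.1 × √(0.16 × 0.25) = 0.12.

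- Hidden HCCs: 1.0 × 0.12 = 0.1; 4.0 × 0.12 = 0.5; 11.2 × 0.12 = 1.3.
- At the lowest pair in Table 2 (70% and 30%), the miss probability is 0.3 × 0.7 + 0.1 × 0.21 = 0.231, and the upper case becomes 11.2 × 0.231 = 2.6.

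AFP-triggered scans and clinical presentation would reduce these numbers further.

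**Step 4: effect on the estimates.** Suppose two double-missed HCCs go unverified, for illustration, with 50 true HCCs.

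- nceMRI: 40/50 = 80% becomes 40/48 = 83.3%.
- USS: 25/50 = 50% becomes 25/48 = 52.1%.
- Difference: 30 points becomes 15/48 = 31.25 points.

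Both missing cases are concordant negative pairs. McNemar's test uses only discordant pairs, so its result does not change.

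**The case against.** The strongest reply is that the text leans one way. Four places, including the visit procedures and schedule that sites follow, give the scan to everyone, and section 11.2 presupposes it. Section 9.8.1 never says that others are excluded; its purpose there is to set the LI-RADS allocation where no follow-up is possible. Section 11.8 is an inclusion rule, not a scanning rule. It also requires attendance at visit 6, where everyone is due a scan, and its alternative may be meant for HCC confirmed after a positive test. This makes the universal reading the likelier intention. It does not remove the contradiction, and 11.8 as worded would let a departure from that intention pass unnoticed.

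A reader might infer more than the documents support:

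- **That cancers after an early false positive are never found.** These participants re-enter surveillance, AFP can trigger a ceMRI, and interval cancers count as false negatives under section 11.2.
- **That the 67 or so participants are missed cancers.** They are HCC-free by construction, and the exact count rests on an inferred correlation.
- **That the bias favours nceMRI because it has more false positives.** A hidden HCC must be negative on both tests, so it leaves both denominators together. No material differential effect on the sensitivity comparison is shown.
- **That 11.8 accepts any earlier ceMRI.** It names a scan after a positive surveillance test, and does not mention one triggered by AFP.

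**Conclusion.** The inconsistency is real and concerns the reference standard for the primary outcome. If 9.8.1 and 11.8 are followed, participants with an earlier false positive can enter the final analysis as HCC-free without verification at month 30. Up to 20–30% of HCC-free participants (50–75 of 250) are in the group with a false positive, fewer once those with current imaging at visit 6 are set aside.

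The likely consequence is small: roughly 0 to 1 hidden HCC (0.1 to 1.3) at sensitivities of 80% and 50%, and 2.6 in the most unfavourable combination examined. This assumes per-participant specificities, a correlation of 0.1, and HCC risk between the 3% floor and 50 in 300. Both sensitivities would be modestly overstated, with little effect on the paired comparison. The point deserves correction because about 50 HCCs carry the sensitivity analysis and a missed final scan cannot be replaced afterwards. It does not threaten the study's main conclusion.

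**What to change.** 1. Reconcile the end-of-study paragraph of section 9.8.1 with the lay summary, sections 7, 9.10 and 11.2, and Appendix A, so that reference-standard verification at month 30 does not depend on earlier surveillance results.
2. State which of the two LI-RADS allocation rules in 9.8.1 applies to a previously positive participant scanned at visit 6.
3. In section 11.8, add that for a participant who re-entered surveillance after a negative triggered ceMRI, that earlier scan alone does not verify HCC-negative status at month 30. Keep the existing 9.8.1 provisions for LI-RADS 3 and 4 lesions under follow-up, and for diagnoses by histology, CT or local MDT consensus. A blanket requirement for a visit 6 ceMRI would conflict with those provisions, which already class unresolved or histologically benign lesions as negative.

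Appendix A already schedules the scan for every participant at visit 6, so no procedure is added to the schedule. The cost is a wording change, and a few participants without a month-30 scan would be reported as unverified instead of HCC-free.
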